- i. Subjects will undergo a full colonoscopy with biopsy for histologic assessment during Screening, and a full colonoscopy or flexible sigmoidoscopy, depending on the extent of disease at Screening, at Week 8. For subjects in Part 2 (Extended Treatment Period), an endoscopy will be performed at Week 16, for this a flexible sigmoidoscopy is recommended, however the use of flexible rectosigmoidoscopy or colonoscopy will be based on the investigator's discretion per local practice.
- j. Appropriate documentation of biopsy results consistent with the diagnosis of UC, in the assessment of the investigator, must be available in order to confirm the subject's eligibility for the study. If this documentation is not available a diagnostic biopsy from the most affected observed area of the colon must be performed during the Screening endoscopy and evaluated by a qualified local pathologist and the results reviewed by the investigator. Biopsies to rule out current dysplasia and colon cancer may be taken during any study endoscopy per the investigator's discretion and evaluated by the local pathologist. During all endoscopies, up to 3 sets of biopsies will be taken (see Section 5.3.1.1 for details about biopsy sampling).
- k. Subjects with normal ECG within 90 days of Screening will not require a repeat ECG, if documentation is available. The Week 8 ECG will serve as the Baseline ECG for Part 2 (Extended Treatment Period), as applicable or for Baseline of Study M14-234 Substudy 3. For subjects who enter Part 2 (Extended Treatment Period), Week 16 ECG will serve as the baseline ECG for Study M14-234 Substudy 3.
- l. Chest x-ray includes posterior-anterior [PA] and lateral views. Subjects with normal chest x-ray within 3 months of Screening will not require a repeat chest x-ray, if documentation is available. In Japan, a CT scan of the chest may be performed in lieu of a CXR, at investigator's discretion.
- m. If a subject had a negative QuantiferON-TB Gold Plus test within 90 days of Screening and source documentation is available, the test does not need to be repeated, provided nothing has changed in the subject's medical history to warrant a repeat test. PPD skin test is only to be used if the site is unable to perform the QuantiferON-TB Gold Plus testing and is to be read 48 to 72 hours after placement.

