#### Clinical Remission

- o per Full Mayo Score: Full Mayo score  $\leq 2$  with no subscore  $\geq 1$ .
- o **per Adapted Mayo Score:** Adapted Mayo score  $\leq 2$ , with SFS  $\leq 1$  and not greater than baseline, RBS of 0, and endoscopic subscore  $\leq 1$ .
- o per Partial Mayo Score: Partial Mayo score  $\leq 2$ , with no subscore  $\geq 1$ .

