#### • Clinical Response

- per Full Mayo Score: decrease in Full Mayo score of ≥ 3 points and ≥ 30% from Baseline, PLUS a decrease in RBS ≥ 1 or an absolute RBS ≤ 1.
- per Adapted Mayo Score: decrease in Adapted Mayo score ≥ 2 points and ≥ 30% from Baseline, PLUS a decrease in RBS ≥ 1 or an absolute RBS ≤ 1.
- per Partial Mayo Score: decrease in Partial Mayo score ≥ 2 points and ≥ 30% from Baseline, PLUS a decrease in RBS ≥ 1 or an absolute RBS ≤ 1.
- o **per Partial Adapted Mayo Score:** decrease in Partial Adapted Mayo score  $\geq 1$  point and  $\geq 30\%$  from Baseline, PLUS a decrease in RBS  $\geq 1$  or an absolute RBS  $\leq 1$ .
- **Endoscopic Improvement:** Endoscopic subscore of 0 or 1.
- Endoscopic Remission: Endoscopic subscore of 0.
- Histologic Improvement: decrease from Baseline in Geboes score.
- **Histologic Endoscopic Mucosal Improvement:** Endoscopic subscore of 0 or 1 and Geboes score ≤ 3.1.
- **Mucosal Healing:** Endoscopic score of 0 and Geboes score < 2.0.

Note: Evidence of friability during endoscopy in subjects with otherwise "mild" endoscopic activity will confer an endoscopic subscore of 2.

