- Multiple Imputation (MI) for NRI-C and HMI: Markov Chain Monte Carlo (MCMC) will be first applied to augment data into monotonic missing pattern, where applicable, and PROC MI will be used to generate 30 datasets using the regression method. The variables to be included in the imputation model are: treatment group, stratification factors (bio-IR status (bio-IR vs. non-bio-IR), Baseline corticosteroid use (yes vs. no) and Baseline Adapted Mayo score ( $\leq 7$ vs. > 7)), Baseline measurement, and if applicable, post-baseline measurements at each visit up to the end of the analysis period. The random seed for MCMC and the random seed for PROC MI are specified in Appendix D. The imputed post-baseline measurements will be rounded to the same precision as the observed data before the determination of responder status. Subjects will be characterized as responders or non-responders based on MI imputed datasets. Using the CMH model adjusted by stratification factors (bio-IR status (bio-IR vs. non-bio-IR), Baseline corticosteroid use (yes vs. no) and Baseline Adapted Mayo score ( $\leq 7 \text{ vs.} > 7$ ), the imputed endpoints will be analyzed using each of the 30 datasets. SAS PROC MIANALYZE will be used to generate the final treatment difference between upadacitinib

treatment group and placebo group and statistical inferences of the risk difference, including hypothesis testing, and 95% CI using Rubin's rule and T-distribution. Note that measurements will be set as missing at or after the occurrence of the UC-related corticosteroids intercurrent event before applying MI. After the MI imputation, an NRI override will be implemented for missing values 1) due to reasons other than COVID-19 infection or logistic reasons, or 2) at or after the occurrence of the UC-related corticosteroids intercurrent event, that is, regardless of MI imputed values, subjects satisfying 1) or 2) will be considered as "non-responder" for binary efficacy.

 As Observed (AO): The AO analysis will not impute values for missing evaluations, and thus a subject who does not have an evaluation on a scheduled visit will be excluded from the AO analysis for that visit. AO will include all values collected in the study.

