## Appendix D. Random Seeds

In case of non-convergence, the random seed will be updated by adding 100000 at each attempt until convergence of model happens.

The missing Mayo subscores are imputed to calculate the Adapted Mayo score, Partial Mayo score, Partial Adapted Mayo score, and Full Mayo score.

Table D-1. Random Seeds for NRI-C

[figure not shown]
	Random Seed		
Endpoints	MCMC Procedure	PROC MI	
Rectal bleeding subscore (0, 1, 2, 3)	21481*	22061#	
Stool frequency subscore (0, 1, 2, 3)	21482	22062	
Endoscopic subscore (0, 1, 2, 3)	21483	22063	
Physician's global assessment (0, 1, 2, 3)	21484	22064	
Geboes grade score (0, 1, 2, 3, 4, 5)	21485	22065	
Geboes Grade 3 subscore (3.1, 3.2, 3.3)	21486	22066	
No bowel urgency (0, 1)	21487	22067	
No abdominal pain (0, 1, 2, 3)	21488	22068	
Fecal Calprotectin (< 150 mg/kg)	21489	22069	
IBDQ response and remission in domain and total score	21490	22070	
PGIC (0, 1, 2, 3, 4, 5, 6)	21491	22071	
PGIS (0, 1, 2, 3, 4, 5, 6)	21492	22072	

\* This is SAS numerical form of Oct 24, 2018, which is the first subject randomized in this study.

Table D-2. Random Seeds for HMI

[figure not shown]
	Randoi	Random Seed		
Endpoints	MCMC Procedure	PROC MI		
Rectal bleeding subscore (0, 1, 2, 3)	21501	22501		
Stool frequency subscore (0, 1, 2, 3)	21502	22502		
Endoscopic subscore (0, 1, 2, 3)	21503	22503		

# This is SAS numerical form of May 26, 2020, which is the last subject randomized in this study.

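### Minor: the imputation model for a COVID-missed Week 8 endoscopic or Geboes score appears to omit the other Week 8 components; adding them is a cheap improvement

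*SAP*

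**What the plan says.** NRI-C is the primary missing-data method for the primary endpoint (SAP 8.4.2) and for the ranked binary endpoints (SAP 8.5.1). Values missing because of COVID-19 are multiply imputed; values missing for other reasons count as non-response.

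SAP 8.3.1 lists the imputation variables as treatment group, bio-IR status, Baseline corticosteroid use, Baseline Adapted Mayo category, and then "Baseline measurement, and if applicable, post-baseline measurements at each visit up to the end of the analysis period". HMI, a sensitivity analysis of the primary endpoint, uses the same model.

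Appendix D states: "The missing Mayo subscores are imputed to calculate the Adapted Mayo score, Partial Mayo score, Partial Adapted Mayo score, and Full Mayo score". Its seed table has a separate pair for RBS, SFS, endoscopic subscore, PGA, Geboes grade and Geboes Grade 3 subscore.

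SAP 3.0 defines the endpoints at issue as conjunctions. Remission needs SFS at most 1 "and not greater than baseline, RBS of 0, and endoscopic subscore" at most 1. Mucosal healing is "Endoscopic score of 0 and Geboes score < 2.0".

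Protocol Appendix C, footnote i, schedules a Screening colonoscopy with biopsy and then "a full colonoscopy or flexible sigmoidoscopy, depending on the extent of disease at Screening, at Week 8", with nothing between them in Part 1. When COVID-19 prevents the Week 8 endoscopy, Protocol 5.1 has the site judge response on the Partial Adapted Mayo score, which is SFS plus RBS. When the endoscopy is done away from the study site, Protocol 5.3.1.1 (biopsy, COVID-19 modifications) waives the study biopsy.

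**The concern.** SFS and RBS have several post-baseline visits, so imputing each from its own history is reasonable. The endoscopic subscore and Geboes score have none before Week 8. On the one-model-per-component reading, their predictors are treatment, strata and the Screening value.

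The protocol itself creates two patterns in which better predictors exist: endoscopy missed with SFS and RBS expected from the diary, and biopsy waived with the endoscopic subscore observed. Drawing the missing component without reference to the observed one treats the two as independent, given treatment, strata and Screening value. If they are in fact positively correlated, too few subjects are imputed as meeting both conditions, in both arms, and the treatment difference shrinks. What is at stake is a small loss in the main estimate of endpoints that combine components.

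**Working it through.** **Plan's own figure.** SAP 2.4 assumes 18% against 5% remission with 308 and 154 subjects and states more than 95% power for a two-sided Fisher test at 0.05. Exact enumeration gives 98.9%, so the statement reproduces.

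**Standard error.** √(0.18×0.82/308 + 0.05×0.95/154) = √(0.000479 + 0.000308) = 0.0281, or 2.8 points. The stratified Mantel-Haenszel estimate in the simulation below has about 2.75.

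**How many could be missing.** The documents give no count. Appendix D supplies two dates: "This is SAS numerical form of Oct 24, 2018, which is the first subject randomized in this study" (21481) and "This is SAS numerical form of May 26, 2020, which is the last subject randomized in this study" (22061). Accrual therefore ran 22061 − 21481 = 580 days. Assume uniform accrual and disruption starting between 1 February and 1 April 2020. Subjects randomized from 56 days before that start had Week 8 at risk: 171/580 = 29% to 111/580 = 19%. An overall missing share of 2% then means 7-10% of at-risk subjects missed endoscopy, 5% means 17-26%, and 10% means 34-52%. The last is an upper bound.

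**Closed-form check.** Let S be qualifying SFS and RBS, and E an endoscopic subscore of at most 1. True remission is P(S and E). Drawing E without its link to S gives P(S)×P(E). With equal marginals and joint rates held at 18% and 5% under a bivariate normal:

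| Correlation | Placebo P(S)×P(E) | Upadacitinib P(S)×P(E) | Difference, points |
|---|---|---|---|
| 0.3 | 2.83% | 13.60% | 10.8 |
| 0.5 | 1.84% | 10.87% | 9.0 |
| 0.7 | 1.11% | 8.25% | 7.1 |

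Loss = missing share × (13 − that difference). At correlation 0.5 and 5% missing: 0.05 × (13 − 9.03) = 0.20 points. At 0.7 and 10%: 0.10 × (13 − 7.14) = 0.59.

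**Simulation.** 1,600 trials per scenario, 30 imputations, normal-regression draws rounded, Mantel-Haenszel difference over 8 strata, Rubin's rules. Only endoscopy is missing, completely at random; SFS and RBS are observed. The model has treatment, three strata and the baseline endoscopic subscore.

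| Correlation | Imputed remission among missing (true about 18% / 5%) | Loss at 2% | Loss at 5% | Loss at 10% |
|---|---|---|---|---|
| 0.2 | 15.0% / 3.6% | 0.04 | 0.09 | 0.16 |
| 0.4 | 12.4% / 2.5% | 0.07 | 0.16 | 0.31 |
| 0.6 | 9.9% / 1.8% | 0.09 | 0.23 | 0.47 |

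The arithmetic agrees: at 0.4 and 10%, 0.10 × (13 − (12.4 − 2.5)) = 0.31. At zero correlation the loss is 0.01-0.02. The largest entry is 0.47/2.75 = 0.17 standard errors. A further simulation gave losses of 0.03-0.11, 0.06-0.25 and 0.10-0.42 points at 2%, 5% and 10%.

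**With Week 8 SFS and RBS added**, the loss is at most 0.04 points in every scenario of the table. A simpler unstratified simulation at correlation 0.5 and 10% missing gave 13.01 with full data, 12.59 component by component and 12.96 with the predictors added. Adding PGA as well changed the loss by at most 0.014. Simulated power is 98.9% or more with and without the predictors. In the closed-form calculation, exact power stays at 98.6% or more.

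**Scale.** NRI-NC loses missing share × 13 = 0.26, 0.65 and 1.30 points.

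**Biopsy missing, endoscopy observed** (true rates assumed; 800 trials per scenario; Monte Carlo SE up to 0.033). At 10% missing and correlations 0.2 / 0.4 / 0.6, histologic-endoscopic mucosal improvement loses 0.08 / 0.24 / 0.50 of about 14-16 points, against at most 0.05 with the endoscopic subscore added. Mucosal healing loses 0.19 / 0.28 / 0.38 of about 5 points, against 0.10-0.12.

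**The case against.** The strongest reply is that the text never restricts the post-baseline measurements to the component being imputed, and that separate seeds prove separate runs, not separate predictor sets. This stands as a limit: the one-model-per-component reading is inferred from the singular Baseline term, the closed list, the seed table and the visit schedule. If the sponsor intends otherwise, the SAP still needs a sentence saying so, because two programmers could build different primary analyses.

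Second, nothing in the conclusions depends on it. That also stands. The bias is toward the null, NRI-NC loses more, and Protocol 5.3.1.1 lets a COVID-affected endoscopy be done within 7 days either side or at another hospital, which makes the higher missing shares less likely.

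Third, the biopsy figures are soft. For histologic-endoscopic mucosal improvement at correlation 0.2, the loss is 0.08 at both 5% and 10% missing, which is compatible with simulation noise. For mucosal healing at correlation 0.2, about half of the loss (0.10-0.12 of 0.19) remains after the fix and is therefore not due to absent predictors.

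A reader might infer that the planned As Observed analysis would expose the problem. The documents do not support that. As Observed also uses data after corticosteroid events (Appendix E) and drops all missing subjects, so its gap from NRI-C mixes several changes. Even in simulations without those complications, its chance difference from NRI-C at 10% missing has a standard deviation of 0.52-0.64 points, larger than the shift sought.

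**Conclusion.** The point holds as a minor improvement to the imputation model. For the primary endpoint the expected shrinkage is roughly 0.03-0.1 of 13 points at 2% missing, 0.06-0.25 at 5% and 0.1-0.5 at 10%. The cruder closed-form figure at correlation 0.7 and 10% missing, 0.59 points or 0.21 standard errors, does not change the grade. The sizes rest on assumed missing shares, assumed positive correlations, and missingness unrelated to outcome.

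Three stronger readings are not supported:

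- **The primary result is at risk.** Power stays near 99%. With no treatment effect both arms are understated alike, so type I error is not threatened.
- **All ranked binary endpoints are biased.** Endoscopic improvement, endoscopic remission and histologic improvement use one component. Bowel urgency, abdominal pain and Week 2 Partial Adapted Mayo response use no endoscopy or biopsy. None is affected in this way. Clinical response per Adapted Mayo was not evaluated.
- **Observed components are ignored altogether.** They still enter the composite: a subject with observed rectal bleeding cannot be imputed a remitter. Only the draw of the missing component lacks the link.

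**What to change.** In SAP 8.3.1, state for NRI-C that the model for a missing Week 8 endoscopic subscore includes Week 8 SFS and RBS, and that the model for a missing Geboes score includes the Week 8 endoscopic subscore. Alternatively, impute the components jointly together with their earlier visits. Only the joint version can help HMI, because the subjects whom HMI imputes generally have no Week 8 values to use as predictors. Keep the non-responder override for corticosteroid events and for non-COVID missingness under NRI-C.

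The cost is a few lines of SAP text and PROC MI code; every predictor is already collected. The downsides are a slightly larger model, an imputation order to state for subjects whose diary is also missing, and a revised seed table in Appendix D if imputation is joint. No visit, treatment or endpoint definition changes.

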8.1.3 Definition of Missing Data Imputation

Missing data will be imputed using one or more of the following methods:

Non-Responder Imputation (NRI): In NRI analyses, subjects who prematurely discontinue the study prior to efficacy assessment at Week 8/Week 16 will be considered non-responders with respect to the efficacy endpoint.

Observed Cases (OC): The OC analysis will not impute values for missing evaluations, and thus a subject who does not have an evaluation on a scheduled visit will be excluded from the OC analysis for that visit.

Depending on the magnitude of missing data due to COVID-19, additional appropriate analysis of missing data may be performed with details included in the SAP.

The SFS and RBS at an assessment visit will be calculated as an average of the entries recorded into the subject's diary from the most recent consecutive 3-day period prior to each study visit. If diary entries from the 3 consecutive days prior to the visit are not available, the 3 most recent consecutive days in the last 10 days will be utilized. If data are not available for 3 consecutive days, the average of the entries from the most recent 3 non-consecutive days in the last 10 days will be utilized. If less than 3 days of diary data are available, SFS and RBS will be considered missing. Clinical endpoints of abdominal pain and bowel urgency from subject diaries will be measured at the same time period as the SFS and RBS.

Subjects in whom UC-related corticosteroids are initiated during treatment (not taken at Baseline) or who have dosages of these medications increased to greater than the dose taken at Baseline will be considered a failure for categorical efficacy endpoints and will have the last values carried forward for non-categorical assessments from that time point through the end of the study.

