#### 2.4 Sample Size Determination

For Part 1, approximately 462 subjects are expected to be randomized to upadacitinib 45 mg QD or placebo in a randomization ratio of 2:1. The sample size for this study is based on the expected proportion of subjects who achieve clinical remission per Adapted Mayo score at Week 8. Based on the results from Phase 2b upadacitinib Study M14-234 (Substudy 1), the proportions of subjects achieving clinical remission per Adapted Mayo score in upadacitinib 45 mg QD group and placebo group are 19.6% and 0%, respectively. Considering the small sample size in Phase 2b study and more stringent definition of primary endpoint used for Phase 3 studies, clinical remission rate is assumed to be 5% in the placebo group and 18% in the upadacitinib 45 mg QD treatment group. Based on these assumptions, a sample size of 154 subjects in placebo and 308 subjects in upadacitinib dose will have > 95% power to detect the 13% treatment difference in the primary endpoint between upadacitinib 45 mg QD group and placebo group using two-sided Fisher's exact test at a 0.05 significant level.

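### The multiple imputation treats discrete Mayo, Geboes and 0/1 items as continuous and then rounds, which misstates imputed responder rates at the cuts that define the endpoints; the effect on the primary result is small

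*SAP*

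**What the plan says.** SAP 8.3.1 first uses MCMC to reach a monotone missing pattern, and then "PROC MI will be used to generate 30 datasets using the regression method". Next comes the rounding step: "The imputed post-baseline measurements will be rounded to the same precision as the observed data". Responder status is set from the rounded values. No logistic, ordinal or predictive-mean-matching option is named, and no lower or upper bound is given.

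SAP Appendix D lists what is imputed: RBS, SFS, endoscopic subscore and PGA on 0-3, Geboes grades, and 0/1 items such as "No bowel urgency (0, 1". The Mayo scores are built from the imputed subscores.

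Several endpoints are cut at 0 (SAP 3.0). Clinical remission requires an RBS of 0. Endoscopic remission and mucosal healing require an endoscopic subscore of 0.

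Appendix D shows integer codes, but Protocol 8.1.3 states: "The SFS and RBS at an assessment visit will be calculated as an average of the entries". With three diary days, observed values can fall in thirds.

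In NRI-C (SAP 8.3.1, 8.4.2, 8.5.1) imputed values count only for COVID-19-related missing data; other missing data are non-response. HMI uses the same imputation model. NRI-NC and As Observed use no imputation model.

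**The concern.** The SAP does not use the word normal, but MCMC data augmentation and the regression method both rest on normal theory, and a categorical model would not need rounding. A normal curve cannot reproduce a pile-up of values at one end of a 0-3 scale, and that is where several endpoints are cut. A single regression containing treatment also gives both arms the same residual SD, which misfits an arm whose scores are bunched.

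Two gaps leave the result to the programmer. A draw that rounds to -1 may be counted as 0 or as a failure of the RBS criterion. For the diary averages, the same precision could mean integers or thirds.

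At stake is the accuracy of the imputed responder rates in NRI-C for the primary and ranked binary endpoints, in the subgroup analyses that use NRI-C, and in HMI. SAP 8.3 aims at reliable estimates of the effect as if the pandemic had not interfered, and this step works against that aim.

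**Working it through.** **1. The plan's own figure.** SAP 2.4: "clinical remission rate is assumed to be 5% in the placebo group and 18% in the upadacitinib 45 mg QD treatment group"; "a sample size of 154 subjects in placebo and 308 subjects in upadacitinib dose will have > 95% power"; "using two-sided Fisher's exact test at a 0.05 significant level". Full enumeration of Fisher's exact test gives 98.9%, consistent with the stated lower bound.

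**2. Ordinal item, closed form.** Assume scores 0, 1, 2, 3 with probabilities 0.60, 0.25, 0.10, 0.05.
- Mean = 0.25 + 0.20 + 0.15 = 0.60.
- Variance = (0.25 + 0.40 + 0.45) - 0.36 = 0.74, so SD = 0.860.
- Integers, negatives counted as 0: Φ((0.5 - 0.60)/0.860) = Φ(-0.116) = 45%.
- Integers, only an exact 0 counted: subtract Φ((-0.5 - 0.60)/0.860) = 10%, which leaves 35%.
- Thirds, negatives counted as 0: Φ((1/6 - 0.60)/0.860) = Φ(-0.504) = 31%.

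The assumed rate of 60% becomes 45%, 35% or 31%, depending on choices the SAP leaves open. On the first reading, other assumed distributions give 30% → 25%, 40% → 31% and 50% → 39%.

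**3. 0/1 item, closed form.** Imputed rate = 1 - Φ((0.5 - p)/√(p(1 - p))).
- p = 0.05: 1 - Φ(0.45/0.218) = 1.9%.
- p = 0.10: 9.1%.
- p = 0.30: 1 - Φ(0.20/0.458) = 33%.
- p = 0.50: 50%.

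Rare items lose badly; mid-range items hardly move.

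**4. Simulation.** A population of 600,000 (2:1) was given assumed subscores at Weeks 2, 4, 6 and 8. Week 8 was imputed by linear regression plus a normal residual and rounded. The comparator was a categorical draw using the same predictors.
- RBS of 0, upadacitinib / placebo: categorical 60% / 30%; rounded 47% / 25% with negatives as 0, or 37% / 21% with exact 0 only.
- Endoscopic subscore 0: upadacitinib 12% → 6.8%; placebo about 2% either way.
- Endoscopic subscore at most 1: placebo 10.0% → 16.4%; upadacitinib 33.9% → 34.4%. A separate check with other assumed distributions and a common SD gave 17% on placebo.

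**5. Effect on the primary difference.** Shift = m × [(rounded - categorical) on upadacitinib - (rounded - categorical) on placebo], where m is the fraction imputed. Remission rates below are in percent, rounded / categorical.

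| Missing | Placebo | Upadacitinib | Shift per imputed subject (points) | m = 2% | m = 5% | m = 10% |
|---|---|---|---|---|---|---|
| Three subscores, negatives as 0 | 1.62 / 1.21 | 8.92 / 11.46 | -2.95 | -0.06 | -0.15 | -0.30 |
| Three subscores, exact 0 | 1.39 / 1.21 | 6.93 / 11.46 | -4.71 | -0.09 | -0.24 | -0.47 |
| RBS only, negatives as 0 | 2.44 / 2.97 | 13.69 / 16.90 | -2.68 | -0.05 | -0.13 | -0.27 |
| RBS only, exact 0 | 1.99 / 2.97 | 10.40 / 16.90 | -5.52 | -0.11 | -0.28 | -0.55 |
| Endoscopy only | 2.20 / 1.36 | 12.19 / 12.06 | -0.71 | -0.01 | -0.04 | -0.07 |

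Remission in the simulated complete data was 3.3% / 17.7% (placebo / upadacitinib). The comparator falls below that because the simulation imputes each subscore without the others; that loss is not charged to rounding.

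The endoscopic endpoints are more exposed. At 10% missing endoscopy, the difference in endoscopic remission moves by 0.10 × (6.8 - 12.0) = -0.52 points. For endoscopic improvement it is 0.10 × [(34.4 - 33.9) - (16.4 - 10.0)] = -0.59 points.

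**6. Power.** Shifting the planned 5% and 18% by these amounts and repeating the Fisher calculation gives 98.4% or more in every scenario.

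**The case against.** The strongest case against is that the step hardly matters where it is used.

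- **Diary items are unlikely to be lost.** RBS, SFS, urgency and pain come from the subject's own handheld device (Protocol 10.3), so a missed site visit does not remove them. What the protocol expects to lose is endoscopy, with response then judged on the Partial Adapted Mayo score (Protocol 5.1), and histology, because the study biopsy is waived at alternative locations (Protocol 5.3.1.1). This stands. It makes the endoscopy-only row the most relevant one for the primary endpoint in NRI-C.
- **The imputation model conditions on more than these checks do.** It includes strata, baseline and, where applicable, other visits. This could reduce the error but would not remove it. It helps endoscopy least: Part 1 has one post-baseline endoscopy (Protocol Appendix C), and entry restricts the baseline subscore to 2 or 3 (Protocol 5.2.1).
- **Planned analyses already avoid the model.** NRI-NC and As Observed cover the primary and ranked binary endpoints. This stands, and lets a reader see whether the imputed values matter. HMI gives no such check.

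A reader might infer more than the documents support:
- That RBS rates collapse as in the thirds calculation. Appendix D lists integers; the conflict with the 3-day average is an ambiguity, not evidence for the larger loss.
- That every 0/1 endpoint, including no bowel urgency, is badly biased. Only rare 0/1 items are, and the documents give no rates for urgency.
- That the plan favours upadacitinib. In every scenario run the primary difference moves toward zero; no false-positive mechanism is shown.

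**Conclusion.** The point holds as a modest technical defect. For imputed subjects, regression plus rounding understates a score of 0 on ordinal items with many zeros, can overstate an endoscopic subscore of at most 1 on placebo, and understates rare 0/1 items. The missing bounds and unclear precision add avoidable programmer discretion.

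The consequence is limited. In NRI-C the primary difference moves by roughly 0.01 to 0.55 points for 2-10% missing, and by at most 0.07 if only endoscopy is missing. Power is not threatened. Ranked endoscopic endpoints move by about 0.5 to 0.6 points at 10% missing. HMI carries the same error into a sensitivity analysis of the primary endpoint.

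All of these sizes rest on assumed score distributions, an assumed missing fraction and, for endoscopy, a residual SD common to both arms. The documents give neither Week 8 distributions nor a count of COVID-19-missing subjects. Improving the step is worthwhile because it is cheap, not because a conclusion depends on it.

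**What to change.** In SAP 8.3.1, replace both the MCMC and the regression steps with fully conditional specification (FCS) in PROC MI. Use logistic models, ordinal or binary, for the discrete items and predictive mean matching for the 3-day averages. Imputed values then stay on the observed scale, and the rounding sentence can go. Changing only the second step to a monotone logistic method is not enough, because the normal-theory MCMC step would remain.

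Where categories are sparse, do not merge across a cut that defines an endpoint. At an assumed 2% of 154 placebo subjects, about 3 would have an endoscopic subscore of 0, and merging 0 with 1 would erase endoscopic remission and mucosal healing. Merge only categories on the same side of the cut, or use predictive mean matching. Align Appendix D with the 3-day averages in Protocol 8.1.3.

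The cost is SAP wording, a changed PROC MI call and some model-fitting work for sparse categories. If data are already unblinded, keep NRI-C as planned and add this as a sensitivity analysis.

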#### 8.4.3 Primary Efficacy Analysis

The primary analysis will compare the proportion of subjects achieving clinical remission in upadacitinib treatment group and placebo group in the ITT1 population. The difference between the treatment groups in the primary efficacy endpoint will be assessed using the CMH test and will be stratified by bio-IR status (bio-IR vs. non-bio-IR), Baseline corticosteroid use (yes vs. no) and Baseline Adapted Mayo score (≤ 7 vs. > 7). A CMH based two-sided 95% confidence interval for the difference between treatment groups will be calculated.

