## 12.0 Overall Type-I Error Control

The overall type I error rate of the primary and the ranked secondary endpoints will be strongly controlled using the fixed-sequence multiple testing procedure. Specifically, the testing will utilize the endpoint sequence of the primary and ranked secondary endpoints in the order as specified in Section 3.1 and Section 3.2 at the  $\alpha$  level of 0.05 (two-sided).

No multiplicity adjustment will be applied to the additional efficacy endpoints listed in Section 3.3. The analysis for additional efficacy endpoints will be performed at the nominal  $\alpha$  level of 0.05 (two-sided).

[figure not shown]
Since there are no efficacy analyses for early stopping planned for the DMC review, no  $\alpha$  spending is needed due to the DMC review.

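### SAP 8.3.1 leaves the deciding p-value under NRI-C to an estimate/SE test on the pooled risk difference rather than the named CMH test; with the usual variances this test is too liberal towards upadacitinib for rare binary endpoints.

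*SAP*

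**What the plan says.** For the primary endpoint, SAP 8.4.3 states: "The difference between the treatment groups in the primary efficacy endpoint will be assessed using the CMH test", stratified by bio-IR status, baseline corticosteroid use and baseline Adapted Mayo score. SAP 8.1 and 8.5.1 name CMH for categorical and binary ranked endpoints, and protocol 8.1.6.1.1 names it for the primary.

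SAP 8.4.2 and 8.5.1 make NRI-C the primary approach for all of these endpoints. Under NRI-C, values missing because of COVID-19 are multiply imputed. SAP 8.3.1 applies the CMH model to each of 30 datasets. It then uses PROC MIANALYZE for the final treatment difference and for "statistical inferences of the risk difference, including hypothesis testing, and 95% CI", by Rubin's rule and a t-distribution. No section says how the 30 CMH statistics become one p-value, or which variance the risk difference carries.

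SAP 12.0 says that the error rate over the primary and ranked endpoints "will be strongly controlled using the fixed-sequence multiple testing procedure" at two-sided 0.05.

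**The concern.** Dividing a Rubin-pooled risk difference by its standard error is a Wald-type test. CMH is a score-type test, with its variance computed under the null hypothesis. The two nearly coincide for common events but separate for rare ones, and unequal allocation makes the gap directional. Under a common rate, the share of the variance of the difference that comes from the placebo arm is (1/154)/(1/154 + 1/308) = 2/3. When the placebo count happens to be low, the difference moves towards upadacitinib and the estimated standard error shrinks at the same time.

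A fixed sequence controls the family-wise error only if each test in it holds its level. SAP 2.4 reports 0% placebo remission in Phase 2b and assumes 5%, so low counts are plausible for at least some endpoints. Endoscopic remission (rank 2) requires an endoscopic subscore of 0. Mucosal healing (rank 10) adds Geboes < 2.0, so it cannot be more frequent than endoscopic remission, and it gates rank 11.

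**Working it through.** **Inputs from the documents.** SAP 2.4: "a sample size of 154 subjects in placebo and 308 subjects in upadacitinib dose", "in a randomization ratio of 2:1"; "clinical remission rate is assumed to be 5% in the placebo group and 18% in the upadacitinib 45 mg QD treatment group"; "two-sided Fisher's exact test at a 0.05 significant level". SAP 8.3.1: 30 imputations, Rubin's rule, t reference. SAP 8.4.3: three binary factors, so 2 × 2 × 2 = 8 strata.

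**Assumptions, because the documents are silent.** The variance of the risk difference (unpooled, Greenland-Robins or Sato); stratum shares (50/40/40% for the three factors, with and without different response rates across strata); share of subjects imputed (1-10%).

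**Step 1: the plan's own figure.** Full enumeration of Fisher's exact test at 5% vs 18% gives 98.9% power, which agrees with "> 95% power to detect the 13% treatment difference in the primary endpoint".

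**Step 2: the two statistics.** Let a = x/308, b = y/154 and p = (x + y)/462.
- Wald: z = (a − b) / √[a(1−a)/308 + b(1−b)/154]
- Null variance (CMH-type): z = (a − b) / √[p(1−p)(1/308 + 1/154)]

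Example, 4/308 vs 0/154: a − b = 0.01299.
- Wald SE = √(0.01299 × 0.98701/308) = 0.00645, so z = 2.01 and p = 0.044.
- Null SE = √(0.00866 × 0.99134 × 0.00974) = 0.00914, so z = 1.42 and p = 0.16. Fisher gives 0.31.

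With no placebo responders, the Wald test is significant from 4/308 and the null-variance test from 8/308.

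**Step 3: exact error rates at 308:154, unstratified.** Nominal 2.5% per direction, 5% two-sided.

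| Common rate | Wald, favours upadacitinib | Wald, two-sided | CMH-type, favours upadacitinib | CMH-type, two-sided |
|---|---|---|---|---|
| 1% | 8.0% | 8.8% | 0.3% | 3.9% |
| 2% | 6.4% | 7.6% | 1.6% | 4.5% |
| 3% | 5.1% | 6.4% | 1.9% | 4.8% |
| 5% | 3.9% | 5.4% | 2.1% | 5.0% |
| 10% | 3.5% | 5.4% | 2.3% | 5.0% |
| 25% | 2.9% | 5.2% | 2.4% | 5.0% |
| 40% | 2.7% | 5.1% | 2.4% | 5.0% |

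**Step 4: eight strata, by simulation.** Error in favour of upadacitinib:
- At 5%: Greenland-Robins 4.2% (6.0% two-sided), Sato 3.9% (5.4-5.5%), CMH 2.0-2.1% (4.9-5.0%).
- At 2%: 5.6-6.4% over the exact and stratified calculations, CMH 1.5-1.6%.
- At 25%: 3.0-3.2% for the two risk-difference variances.

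Different response rates across strata barely changed these results.

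**Step 5: Rubin's rules.** With Q the mean difference, Ū the mean within-dataset variance and B the between-dataset variance, T = Ū + (1 + 1/30)B and t = Q/√T. With 1-10% of subjects imputed:
- At 5%: 3.8-4.0% in favour of upadacitinib, 5.3-5.5% two-sided.
- At 2%: 5.3-5.9% in favour of upadacitinib.
- At 5% with a null variance in place of Ū: 2.0-2.1% and 4.7-4.8%.

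Imputation therefore does not remove the asymmetry; the choice of variance does.

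**Step 6: the design point.** At 5% vs 18%, power is 99.4% (Wald) and 99.0% (null variance). The two reach different decisions in 0.34% of trials. With 8/154 placebo responders, the thresholds are 31 and 33 of 308.

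**The case against.** The strongest reply is that SAP 8.3.1 names no variance. It speaks of the CMH model in each dataset, and 8.5.1 points to 8.3.1 as the place where the CMH analyses are specified. A standard error back-calculated from the CMH statistic would remove the excess. This stands: inflation is shown for the usual variances, not for the text as such. It also means that the text does not determine the deciding statistic.

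Testing the risk difference also matches the estimand and keeps p-value and interval consistent. That is a real advantage, but it does not make the test hold its level.

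On size, the SAP's level is two-sided, and at the planned 5% rate the two-sided error is only 5.4-6.0%. The 1-2% rates are not the plan's: SAP 2.4 deliberately assumes 5% despite the 0% in Phase 2b. A false positive also needs upadacitinib to be equally rare, and rank 10 is reached only after the primary and nine ranked endpoints have succeeded. These points stand and limit the practical risk. CMH is itself conservative towards upadacitinib at about 1% (0.3% against 2.5%), so neither test is well calibrated there.

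NRI-NC and As Observed involve no imputation, so CMH applies directly and a discrepancy would be visible. They are not the confirmatory analysis, however, and no rule says what a disagreement would mean.

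**Conclusion.** The concern holds in a limited form. The SAP names CMH, but for its primary approach it describes an estimate/SE test with no stated variance and no rule for pooling the CMH statistics. With the usual variances, the error in favour of upadacitinib is about 3.9-4.2% at a common 5% rate and 5.6-6.4% at 2% (5.3-5.9% once some subjects are imputed), against a nominal 2.5%. The stratified results rest on assumed stratum shares and the Rubin results on an assumed imputed fraction; within each method, varying these inputs left the direction of the excess unchanged.

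A reader might infer that the p-values for the primary and every binary ranked endpoint fail error control. The documents do not support that. The variance is open, the excess is small at 25% or more, and the primary result at 5% vs 18% hardly depends on the choice. Endoscopic remission and mucosal healing are only possible cases, because the documents give no rates for them. This should be fixed, but it is not a condition for the trial's validity.

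**What to change.** In SAP 8.3.1, separate the test from the interval:
- State that the p-value deciding each step of the fixed sequence in SAP 12.0 comes from the stratified CMH test pooled over the 30 imputations. Either pool the CMH score (observed minus expected upadacitinib responders) with its null variance by Rubin's rules, or combine the CMH chi-squares after a Wilson-Hilferty transformation. Name one.
- Keep the Rubin-pooled risk difference for the point estimate and 95% CI, and name its variance estimator.

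Settle this before treatment assignments are released for analysis. A later choice between two documented tests could be driven by the data.

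The cost is one paragraph, a small program change and 99.4% − 99.0% = 0.4 points of power at the design point. The p-value will be less favourable for very rare endpoints, and p-value and interval may occasionally disagree near the boundary; the SAP should say that the p-value then decides.
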